10. STUDY ENDPOINTS*

- The primary outcome measures are from study Aim I: Feasibility and safety of intervention will be measured through ongoing observation and safety logs and monitoring of recruitment/ retention. Acceptability will be assessed with activity evaluation surveys, focus groups at study conclusion and a follow-up personal interview/ phone call to assess bird feeder use.
- The secondary outcome measures are from Aim II and Aim III: Psychological well-being will be assessed at baseline and after each activity through: Warwick-Edinburgh Mental-Well Being Scale (14 item; $\alpha=.91$)^{44, 45}, Speilberger State/Trait Anxiety Inventory (6 item; $\alpha=.82$)⁴⁶ and Center for Epidemiologic Studies Depression (CES-D-10) scale (10 item; $\alpha=.70$).⁴⁷ We will measure physiological parameters (heart rate via wearable wrist biosensor)⁴⁸ at baseline with F/U heart rate both before and after each activity. We will

INVESTIGATOR STUDY PLAN - REQUIRED

also obtain the PCL-5 at baseline and a follow up measure of the PCL-5, at study conclusion.^{23, 24} Connection to nature and wildlife will be measured at baseline and after each activity through: the short-form Nature-Relatedness (NR-6) (6 item; $\alpha=.85-.96$)⁵⁰ and Transcendent Feelings of Animal Valuation Scale developed by PI (7 item; $\alpha=.84-.94$).²⁰ Qualitative assessment will include an animal observation journal exercise during the Maine Wildlife Park activities.

There are no safety endpoints.

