11. PROCEDURES INVOLVED*

Approach

The feasibility nature of this study offers flexibility to evaluate a series of immersion activities. We will use a crossover design in which each participant receives a sequence of 3 wildlife-immersion activities and serves as his or her own control.³⁷ The use of crossover designs has been suggested for future AAI studies.³ The intervention will include an introductory forest walk followed by 3 wildlife immersion activity experiences in different settings that offer different ways to experience wildlife. All activities will be guided by field experts and include education to ensure safety for human subjects as well as animals. Wildlife education programs have been shown to reduce fear and enhance self efficacy about managing encounters with wildlife.^{38, 39} Each activity will be conducted twice to minimize potential anxiety and novelty effects.

Activities will be planned in small groups (up to 10 participants) to provide more concentrated experience at facilities and peer support. We will endeavor to maintain same groups throughout although logistical modification may sometimes be needed.

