Surveys with ID numbers will be conducted using pen and paper and collected by PI immediately afterwards. Quantitative data will be entered into SPSS version 24 by research assistant and/or PI using double data entry. Focus group audiotapes will be transcribed by a transcriptionist using Microsoft word files. All data will be stored in a password-protected institutional research drive with access limited to investigators and research assistant. Hard copies will be kept in locked file/office.

Analytic Plan

Sample size and power: Because pilot studies do not provide meaningful estimates of effect sizes for between-condition comparisons, due to the imprecision inherent in small samples^{51,52} we base our proposed sample size of 50 participants – anticipated average of 10 per group – on pragmatics of recruitment, retention, and examination of feasibility, acceptability, and safety, providing important information for planning a future R01 study. Taking retention as an illustrative Aim 1 outcome, a 95% confidence interval is (35.5%, 64.5%) for a rate as low as 50% seen in the PTSD literature,² and (66.3%, 90.0%) for 80% retention. [name] (Co-I) has a long standing relationship of working with Soldier On and has obtained follow up rates above 80% in other studies.⁵³ For Aim 2-3 analyses, we adjust the sample size for possible within-group correlation (intra-class correlation, ICC) using $ICC=0.0105$ from a prior study of mindfulness.⁵⁴ Applying the resulting design effect⁵⁵ of $1+0.0105 \times (10-1)=1.0945$ and 80% retention rate yields an effective sample size of $40/1.0945=36$ participants. With an overall 0.05 Type I error rate and a Bonferroni correction for multiple testing (6 pairwise comparisons of the 4 activities), and 80% power, we will be able to detect a statistically significant mean within-participant between-activity difference in an outcome, e.g., anxiety, of 0.56 SD, where SD indicates standard deviation of within-participant change in the outcome. The corresponding detectable within-participant change from baseline to end of study or baseline versus each individual activity (no corrections for multiple testing), is 0.48 SD.

Statistical analyses:

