Aim 1: To assess feasibility, we will estimate quantities relevant for study planning, including outcome standard deviations and within-participant and within-group correlations, and rates of attrition and missing data and their correlates. Acceptability of each activity will be assessed by tabulating evaluation surveys responses. Safety for each activity will be assessed via the per-participant distribution of incidents reported by severity. Analyses will be conducted for the full sample as well as by gender.

Aim 2: We will conduct preliminary intent-to-treat analyses comparing participant outcomes across activities and baseline using linear mixed modeling⁵⁶ with a random effect for participant group and accounting for within-participant correlation over time. In addition, the role of novelty for each activity will be estimated as within-participant differences in physiologic outcomes between the first and second time that activity is conducted. To the extent possible given sample sizes, we will adjust for participant characteristics predictive of missing data to reduce nonresponse bias.⁵⁷ Gender differences will be examined by including gender as a covariate, and its interaction with activity to explore effect modification; by necessity, the latter analyses will be exploratory.

Aim 3: Analyses parallel to those in Aim 2 will compare participants' connectedness to nature and wildlife across activities. Additional exploratory analyses will examine whether connectedness to nature and wildlife mediates between-activity differences in well-being in Aim 2 analyses.

INVESTIGATOR STUDY PLAN - REQUIRED

Our estimates of retention, intra-group and within-participant correlation, standard deviations, and preliminary effect sizes and novelty effects, as well as expert opinion and literature, will inform the design of a future larger crossover study, including recruitment and selection of activities to be evaluated. This future study will randomize participants to ordering of activities (not feasible in this pilot study), permitting formal assessment and analytic treatment of possible carryover effects.⁵⁸ Interestingly, a meta-analysis suggests that effect sizes for AAI do not vary greatly by aspects of study design,¹ suggesting that estimates from our non-randomized-order pilot will be informative for future planning.

Qualitative analysis:

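### Does the Aim 2 mixed model drop the within-group clustering that the power calculation allows for?

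*Combined protocol and SAP*

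**What the plan says.** In Section 13, under Sample size and power, the plan says of Aims 2 and 3: "we adjust the sample size for possible within-group correlation (intra-class correlation, ICC" = 0.0105). The resulting design effect of 1.0945 and 80% retention give an effective sample of 36. Detectable differences are then quoted in SD units, "where SD indicates standard deviation of within-participant change in the outcome". The uncorrected figure for change from baseline to end of study, or "baseline versus each individual activity (no corrections for multiple testing), is 0.48 SD".

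Under Statistical analyses, the Aim 2 model is a linear mixed model "with a random effect for participant group and accounting for within-participant correlation over time". Aim 3 uses parallel analyses. Nothing says whether the group effect is an intercept, a group-by-activity term or a group-by-session term.

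On the groups themselves, Section 11 says: "Activities will be planned in small groups (up to 10 participants) to provide more concentrated experience at facilities and peer support". It adds: "We will endeavor to maintain same groups throughout although logistical modification may sometimes be needed".

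On the standing of these analyses, Section 10 says: "The secondary outcome measures are from Aim II and Aim III". The primary outcomes are feasibility, safety and acceptability.

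**The concern.** The power paragraph applies a clustering penalty to within-person change. That penalty is needed only if people in the same group change together. A reader who takes the model's group effect to be the usual random intercept will see a mismatch. The intercept is the same at every occasion, so it disappears when one activity is compared with another. The within-participant covariance does not replace it, because it links one person's repeated measures and not the measures of people who attend together.

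If co-attendees share a good or bad day, standard errors for activity contrasts would be too small and the tests too liberal. The planning output could also be affected. A future design effect on within-person change needs the within-group correlation of change, and the plan does not say whether the correlation it will report is of levels or of change.

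**Working it through.** **Inputs.** From Section 13: 50 participants, about 10 per group (so about 5 groups); 80% retention (40 people, 8 per group); ICC 0.0105; 80% power; 5% type I error, divided by six for activity comparisons. From Section 11: four activities, each run twice, so eight sessions.

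**1. The plan's figures.** Design effect = 1 + 0.0105 × (10 − 1) = 1.0945. Effective n = 40/1.0945 = 36.55, taken as 36. A paired t test (noncentral t, two-sided 5%, 80% power) detects 0.480 SD with n = 36, which matches the stated 0.48. Without the penalty, n = 40 gives 0.454 SD. The allowance therefore moves the detectable change by about 0.03 SD.

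**2. What cancels.** Write the outcome of person *i* in group *g* at session *s* as μ_s + b_g + p_gi + w_gs + e_gis. The difference between two sessions removes b_g (group intercept) and p_gi (person). What remains is w_gs − w_gs′ plus individual error. A model without w treats it as independent error. If w has zero variance, so that only levels cluster, that model is correct.

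**3. Size at the plan's ICC, read as an ICC of change.** The SE is too small by the factor 1/√DE, and type I error is 2{1 − Φ(z/√DE)}.
- 8 per group: DE = 1 + 7 × 0.0105 = 1.0735; SE ratio 0.965; 1.960/1.0361 = 1.892, so 5.9%. At 0.05/6 = 0.83% it becomes 1.1%.
- 10 per group: DE = 1.0945; SE ratio 0.956; 1.960/1.0462 = 1.873, so 6.1%. At 0.83% it becomes 1.2%.
- 8 per group, with the shared effect persisting over both runs of an activity: the ICC of the two-run contrast is 2 × 0.0105/(2 × 0.0105 + 0.9895) = 0.0208; DE = 1 + 7 × 0.0208 = 1.146; 1.960/1.070 = 1.831, so about 6.7%.

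**4. Would a group-by-session term do better?** Simulation of 5 groups × 8 people × 8 sessions, contrasting two activities each averaged over two sessions, with the variance estimate truncated at zero. ICC here is the share of within-person session-to-session variance that co-attendees have in common. Values above 0.0105 are assumptions. Type I error at nominal 5%:

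| ICC | Shared effect | Intercept only | With group-by-session term |
|---|---|---|---|
| 0 | none | 5.0% | 3.9% |
| 0.0105 | session-specific | 5.9% | 4.3% |
| 0.0105 | persists by activity | 6.9% | 5.0% |
| 0.05 | session-specific | 9.3% | 4.8% |
| 0.05 | persists by activity | 14.2% | 8.7% |
| 0.10 | session-specific | 13.6% | 5.0% |
| 0.10 | persists by activity | 22.2% | 11.7% |

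**5. Price of the extra term (session-specific effect).** Power for a 0.48 SD difference at 5% falls from 85.6% to 82.0% at ICC 0, and from 84.9% to 79.9% at 0.0105. Intervals widen by 7% and 9% on average. The variance estimate is zero or negative in 53% and 42% of samples, and the model then reduces to the intercept model anyway.

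**The case for a change.** The strongest case for acting is that 0.0105 is borrowed from a mindfulness study. The plan does not say whether it describes levels or change, and nothing shows that it fits small groups who travel, learn and watch animals together. A shared session effect is plausible, and at an assumed ICC of 0.05 or 0.10 the intercept model is clearly too liberal. The pilot also exists to supply planning inputs, and one sentence would settle the matter.

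Part of this stands. The form is unstated, the true ICC is unknown, and at larger ICCs the extra term beats a bare intercept. Three things limit it.
- No larger ICC appears in the documents, and the wording already leaves room for a richer group term.
- The group-by-session term is not a safe default. If the shared effect persists over both runs of an activity, it also exceeds 5% at those ICCs. With about five groups, choosing between the forms in advance is largely a matter of preference.
- The planning output is not closed off. Aim 1 promises planning quantities that include "outcome standard deviations and within-participant and within-group correlations", and that list is open-ended. The same data yield the correlation of levels and of change. Either will be imprecise: at a true ICC of 0.0105, 95% of estimates of the ICC of change run from −0.055 to 0.090.

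**Conclusion.** No change follows. The observation is accurate: the penalty is applied to change, the form of the group effect is unstated, and an intercept alone would cancel. But the power paragraph allows for a *possible* correlation. That is a precaution, and it does not commit the analysis to clustered change.

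On an intercept-only reading with 5 groups of 8, there are two cases. If only levels cluster, the analysis is valid and the quoted 0.48 SD is conservative by about 0.03 SD. If change clusters at the plan's ICC, nominal 5% becomes 5.9% to just under 7%. Against a session-specific effect at that ICC, the alternative model swaps about one point of excess for a little under one point of conservatism, at a cost in power and precision. It comes out ahead at the plan's ICC only if the effect persists by activity.

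Little rests on the result. Section 13 bases the sample of 50 on practical grounds and calls the Aim 2 comparisons preliminary, and the primary outcomes do not use this model. Section 23 gives the final analysis plan to a co-investigator responsible for the statistics, which is where a random-effects structure is normally settled. The conclusion assumes balanced groups that stay together and an ICC of change near 0.0105. A much larger ICC would make the choice of form matter more.

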14. PROVISIONS TO MONITOR THE DATA TO ENSURE THE SAFETY OF SUBJECTS*

The principal investigator (PI) will be responsible for monitoring safety in this study. The PI will accompany study activities and maintain a safety log to report all incidents. Safety will be monitored on an ongoing basis. The safety log will be reported to the Safety Officer ([name]) on a monthly basis. An interim analysis report will be conducted after Year I or as indicated by regulations. Serious adverse events will be reported to the Safety Officer and IRB immediately. Analysis of any adverse events will be conducted with modification of protocol if indicated. Further details are provided in the data and safety monitoring plan document.

Safety Log

| | Date/ Time | No. of participants in activity | Safety incident | Etiology | Intervention for participant/ animal if needed | Modifications to protocol if needed | IRB Notification |
|----------------------------|------------|---------------------------------|-----------------|----------|--|-------------------------------------|------------------|
| Intro Forest Walk | | | | | | | |
| Time 1 | | | | | | | |
| Time 2 | | | | | | | |
| Wildlife Activity I | | | | | | | |
| Time 1 | | | | | | | |
| Time 2 | | | | | | | |

INVESTIGATOR STUDY PLAN - REQUIRED

| | | | | | | | |
|------------------------------|--|--|--|--|--|--|--|
| Wildlife Activity II | | | | | | | |
| Time 1 | | | | | | | |
| Time 2 | | | | | | | |
| Wildlife Activity III | | | | | | | |
| Time 1 | | | | | | | |
| Time 2 | | | | | | | |

Psychological Evaluation: The PCL-5 will be conducted at baseline and post study. A Soldier On mental health counselor will be available by phone during the administration of the PCL-5 test in case the test exacerbates any psychological symptoms. Psychological surveys will be entered within one week and monitored for significant increase. If any individuals have a high baseline score for anxiety or depression at study enrollment (as defined in literature) or a > 25% increase over baseline anxiety or depression scores, the participant will be referred for counseling at Soldier On via contacting the individual's Soldier On Case Manager. The case manager will be contacted via a secure email using "SEND SECURE" in the subject line. The email will include the participant's first name and last initial, name of test, normal test parameters, participant's score and comparison to baseline if applicable. Participants with any medical or psychological symptoms that occur during the activities will be referred to clinical services at Soldier On (which has clinical staff) or VA (which is located at same campus as Soldier On) via referral to the case manager. If any participants notify staff of exacerbation of psychological symptoms between activities, they will also be referred to Soldier On/ VA services. If an urgent medical or psychological issue occurs in the field, the study team would call 911 to have them transferred to closest hospital facility. The protocol will be finalized with the study advisory board once convened.

15. WITHDRAWAL OF SUBJECTS WITHOUT THEIR CONSENT*

Participants may be withdrawn from study without their consent if they exhibit behavior indicating active addiction or intoxication which is in violation of the inclusion criteria or if they engage in behavior which places any other participants or study staff at risk or if they engage in animal cruelty behaviors. Additionally they may be removed if they:

- Have an adverse event that requires stopping the research
- The research is canceled by the FDA or the sponsor
- Are unable to attend the activities as scheduled.

16. RISKS TO SUBJECTS*

Risks include:

- Potential loss of identifiable data
- Animal bite or scratch
- Exposure to animal disease

INVESTIGATOR STUDY PLAN - REQUIRED

- Exacerbation of psychological symptoms
- Psychological distress due to seeing injured, dying or deceased animals
- Substance abuse exacerbation
- Triggering of psychological symptoms due to unexpected noises in external environment
- Tick bite during outdoor walk
- Allergy exposure
- Sun exposure
- Fatigue/ dehydration during activities
- Traffic accident in route to or from activity
- Contracting Covid-19

Protection against risks

Recruitment and Informed Consent

The PI will meet with each potential participant to review the study including potential risks and benefits. Participants will provide informed voluntary consent.

Participants will be accompanied during activities by the PI, a registered nurse. All wildlife-related activities will be preceded by education and guided by an expert in wildlife care. Risk-specific preventative measures will be taken as below. If any unexpected adverse events occur the event will be given immediate attention at the site (such as first aid if needed) and participant will be referred for appropriate medical or psychological care. The PI will bring a first aid kit and Narcan nasal spray as a precaution for all activities.

All study sites are < 19 miles from a local hospital (ranging from on site to 18.1 miles)

- Soldier On (On campus of VA Hospital in Pittsfield, MA)
- Harvard Forest-Athol Memorial Hospital (4.2 miles)
- Mass Audubon Broad Meadow Brook- UMass Memorial Medical Center (4.9 miles)
- Maine Wildlife Park-Central Maine Medical Center (18.1 miles-highway interstate travel)

Confidentiality: The following steps will be taken to ensure that all patient data remain confidential.

(1) *Use of numeric identifiers:* To ensure confidentiality, study assessments and electronically stored data will be identified only by a unique identifier. The master list linking the patient ID to the patient's identifying information will be maintained in a separate file and will be destroyed at the conclusion of the study. Signed consent forms will be kept in locked filing cabinets and will only be accessible to the PI and staff listed on the IRB approval.

(2) *Data storage:* No identifying information will be stored with survey responses, or within the analytic database. All paper data collection documents will be stored in locked file cabinets within locked offices that are accessible only to the project investigators and staff. Signed consents will be kept in a separate file from participant data. Access to the electronic data will be restricted to investigators and research staff using a designated research drive. Electronic data will be password protected to guard against unauthorized access.

(3) *Staff training:* All project staff will pass the CITI exam on ethical conduct of research. Any newly hired study staff will pass the web-based CITI exam as required by the University of

INVESTIGATOR STUDY PLAN - REQUIRED

Massachusetts Medical School Institutional Review Board for the Protection of Human Subjects. In addition, study staff will receive training and supervision regarding patient confidentiality. This training will be directed by [name]. The training will address the rights of patients to keep participation decision (yes or no) and all assessment data private and confidential. Training will also emphasize that discussion or disclosure of *any* information obtained from research participants during the course of the study is strictly prohibited. Prior to having any direct contact with research participants, the project assistant will receive training in recruitment and assessment procedures.

(4) *Handling of published data and reports:* Published data derived from this study will consist of statistical analyses collapsed (averaged) across participants. Qualitative data will contain direct quotes that participants have shared but no personable identifiable information will be linked to the quote. Under no circumstances will data from individual participants be identifiable in reports or published manuscripts.

| Risk | Protective Measures |
|--|--|
| ➤ Potential loss of identifiable data | ➤ As described above. |
| ➤ Animal bite or scratch | 
 ➤ Proper instruction prior to activities ➤ Follow facility protocols ➤ In the event of incident, first aid will be applied and participant will be referred to VA facility at Soldier On for follow up ➤ PI will undergo wilderness first aid course prior to study initiation |
| ➤ Exposure to animal disease | 
 ➤ Use of gloves in wildlife veterinary hospital ➤ Follow facility protocols ➤ No activities with animals in isolation ward ➤ No handling of raccoons due to being rabies vector ➤ Exclusion of individuals with severe immunocompromised status ➤ Instructions for handwashing provided |
| ➤ Exacerbation of psychological symptoms | 
 ➤ The PCL-5 test will be administered by the PI, a registered nurse, with a mental health clinician from Soldier On available by telephone in the event that any individuals develop psychological symptoms when taking the test ➤ Ongoing assessment by PI, RN ➤ An action plan will be developed with Soldier On for acute referral for any psychological distress; for stable symptoms we will notify the individual's case manager at Soldier On for referral to appropriate services including VA located by Soldier On; for acute emergency in |

INVESTIGATOR STUDY PLAN - REQUIRED

| | |
|---|---|
| | the field PI will call 911 for patient to be brought to local ED. The case manager will also be notified if any field emergencies occur. |
| ➤ Psychological distress due to seeing injured animals | ➤ Animals on exhibit at Maine Wildlife Park are largely healthy ➤ At New England Wildlife Center we will focus activities primarily on healthy babies and animals with stable injuries. |
| ➤ Substance abuse exacerbation (we anticipate some of population will have co-morbidities of substance abuse) | ➤ Inclusion criteria of 30 days or more free of drugs or alcohol abuse and willingness not to use substances before or during activities ➤ Participants will be instructed not to use substances before or during activity trips; if any participants arrive for activity with signs of being under the influence of substances they will be asked to stay home that day; if any participants become impaired due to substance use during activities they will be asked to stay near van under observation of Soldier On project assistant. ➤ If any participants notify staff of exacerbation of psychological symptoms between activities, they will be referred to Soldier On/ VA services via notification of case manager. ➤ If any substance abuse exacerbation occurs during the activities participants will be referred to Soldier On/ VA services via notification of case manager. ➤ If any participant becomes physically or cognitively compromised the PI will call 911 for transport to local ED. ➤ PI will carry Narcan nasal spray in the event of participant overdose; PI will undergo training prior to study implementation |
| ➤ Triggering of psychological symptoms due to unexpected noises in external environment. | ➤ Due to the potential for distant gunfire from a rural gun club or seasonal hunters near the Harvard Forest (as well as a wide range of possible noises in any public environment) we have included that risk in the consent form and added a question to the activity evaluation regarding stress from environmental sounds/ events. Additionally, the PI has contacted the gun club to ascertain that no large scale target shooting events are scheduled during the times when the study activities will take place. |

INVESTIGATOR STUDY PLAN - REQUIRED

| | |
|--|---|
| ➤ Tick bite during outdoor walk | ➤ PI will bring tick spray on all activity trips and will encourage use by each participant ➤ Participants will be instructed to monitor self for tick bites following activity and to call VA MD if any bites occur |
| ➤ Sun exposure | ➤ Although outdoor activities will primarily be in shaded areas PI will provide participants with sunscreen as a precaution |
| ➤ Allergy exposure | ➤ Participants with severe outdoor allergies excluded; participants with mild-moderate allergies encouraged to take medication prior to outdoor activities |
| ➤ Fatigue/ dehydration from activities | ➤ A boxed lunch will be provided each day along with ample bottled water |
| ➤ Possible traffic accident in route to or from activity | ➤ Use of drivers and vehicles owned and operated by Soldier On or Professional bus/ van service |
| ➤ Contracting Covid-19 | 
➤ We will include only individuals that have been:
 
(A) fully vaccinated for Covid-19 and are up to date with booster. Fully vaccinated is defined by the CDC as:
 
 ○ 2 weeks after second dose in a 2-dose series, such as the Pfizer or Moderna vaccines, or ○ 2 weeks after a single-dose vaccine, such as Johnson & Johnson's Janssen vaccine 
*Up to date = 1 booster when eligible
 
https://www.cdc.gov/coronavirus/2019-ncov/vaccines/stay-up-to-date.html
 
OR
 
 ○ (B) Partially vaccinated against Covid-19 and willing/able to (a) complete a home antigen test for Covid-19 on the morning of each activity and report results to the PI prior to transportation departure and (b) willing to wear a mask during transportation to and from the activity. Antigen tests and masks will be provided to participants who meet this criteria. ● Individuals who have been vaccinated but who have a condition or take medications that weaken their immune system will be advised to follow their physician's recommendations regarding any additional precautions. |

INVESTIGATOR STUDY PLAN - REQUIRED

| | |
|--|--|
| | 
 • We will follow all Covid-19 precautions as indicated by state and institutional policies/guidelines as well as Soldier On policies. • Individuals who develop Covid-19 symptoms or have a positive antigen test prior to a scheduled activity will be asked to self-exclude from attending that activity, notify research assistant and to contact their health care provider. These symptoms include: Fever or chills; cough; shortness of breath or difficulty breathing; fatigue; muscle or body aches; headache; new loss of taste or smell; sore throat; congestion or runny nose; nausea or vomiting; or diarrhea. https://www.cdc.gov/coronavirus/2019-ncov/symptoms-testing/symptoms.html • Individuals who have been diagnosed with Covid-19 or exposed to a person with Covid-19 will be asked not to participate in activities until their isolation/ quarantine period is over. |
|--|--|

